**Table 2. Demographics of dbGaP projects used in discovery sample.**

Project	Sex	Age Range	Age M(SD)	Ethnicity/Race
ADGWAS	46.9% F, 53.1% M	18-79	37.4 (11.8)	35.1% ED, 64.9% EM
COGA	53.7% F, 46.3% M	18-97	39.83 (14.6)	65.8% ED, 26.2% EM
COGEND	61.8% F, 38.2% M	25-47	36.5 (5.5)	55.4% ED, 44.6% EM
FSCD	50.3% F, 49.7% M	18-60	37.0 (8.8)	48.3% ED, 51.7% EM
GWASHD	47.0% F, 53.0% M	18-58	35.6 (9.2)	100% ED

ED=European-Descent, EM=Ethnic-Minority

Genotyping and imputation. Participants provided blood samples to biologic repositories, on which whole-genome genotyping was performed. Several genome-wide Illumina arrays were used, including the Human OmniExpress 12.VI, the Omni2.5 BeadChip, and the Human610-Quad BeadChip.] Genotypic data were checked for minor allele frequency (SNPs excluded with frequencies < 3%), pedigree structure/Mendelian inconsistencies, with samples imputed to 1000 Genomes using SHAPEIT and then IMPUTE2.

[figure not shown]
Phenotype measures. Participants completed the Semi-Structured Assessment for the Genetics of Alcoholism (SSAGA) [or variants of this instrument (e.g., Semi Structured Assessment for Drug Dependence and Alcoholism) that included our specific questions-of-interest]. The SSAGA includes reports of whether participants have previously performed physically-aggressive acts, and whether the acts were performed while participants had consumed alcohol or not (e.g., “have you ever physically injured anyone on purpose?”). Greater alcohol-influenced aggression is indicated by a greater number of yes (with alcohol) responses to such questions and non-alcohol-influenced aggression is indicated by a greater number of yes (no alcohol) responses. The SSAGA also assesses the extent to which participants have previously engaged in specific aspects of alcohol misuse (e.g., binge drinking).

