**Figure 2. Competing conceptual models of the heritability of alcohol-influenced aggression.**

aggression, and alcohol misuse. Fixed-effects covariates will include age, ethnicity/race, sex, and socioeconomic status. To prevent heritability inflation, any two participants who share a second-cousin degree of relatedness or more will be excluded from subsequent analyses. A heritability ( $h^2$ ) estimate will be calculated for alcohol-influenced aggression, *controlling* for the heritability of non-alcohol-influenced aggression and alcohol misuse phenotypes. A substantial heritability estimate ( $h^2 > 0.1$ ,  $p < .05$ ) for alcohol-influenced aggression will serve as support for the unique genetic basis for this phenotype.

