**Genome-wide association study (GWAS).** After the GCTA, GWAS will be used to identify single nucleotide polymorphisms (SNPs) and clusters of SNPs that are significantly associated with alcohol-influenced aggression. Due to the skewness of the alcohol-influenced aggression scores (see Figure 3), quasi-Poisson regression analyses will be used to accommodate such a distribution using the Bioconductor v2.1 package and SNPTEST v2.5. Specifically, alcohol-influenced aggression scores will be regressed onto principal components of the available SNPs using an additive model, excluding non-autosomal SNPs, with demographics factors as covariates. Due to racial stratification, separate GWAS will be performed for participants of African, American, East Asian, European, South Asian, and Mixed Race descent. Participants will be empirically assigned to these ancestral super-populations using the 1KGP population base and the Mahalanobis' distance between each population. I will meta-analyze these separate sets of GWAS findings METAL v3.0^32, which will produce meta-analytic '% variance explained' effect size estimates and  $p$  values for each SNP. [In addition to this meta-analytic approach, I will test for gene-by-race/ethnicity moderation using a kernel-machine approach to estimate whether each SNP's association with alcohol-influenced aggression varies across the discovery sample's diverse racial/ethnic groups, using the Robust Joint Tests package.] After correction for genetic inflation and weighting based on sample size, I will calculate polygenic risk scores for alcohol-influenced aggression [based on SNPs meeting increasingly stringent significance thresholds: .5, .4, .3, .2, .1, .05, .01, .001, .0001. The threshold that maximizes the variance explained ( $R^2$ ) in alcohol-related aggression will be used for risk score calculation.] Using an additive approach, I will sum across the number of alleles that are significantly linked to the phenotype, weighted by their respective effect size estimates from the GWAS. For example, if the A allele (versus the corresponding G allele) of a given SNP is significantly associated with greater alcohol-influenced aggression, then each copy of the A allele will be initially coded as +1 (GG = 0, GA = 1, AA = 2). These scores will then be multiplied by the GWAS effect size estimate for that given SNP. This polygenic risk scores will capture aggregate genetic risk for alcohol-influenced aggression in a manner that represents the current state of the field.

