#### **Feasibility**

Preliminary phenotypic analyses on the alcohol-influenced aggression scores from the COGA dataset, assessed among a subset of 9,273 participants, revealed a substantially-variable, albeit positively-skewed, distribution of alcohol-influenced aggression (Figure 3). Scores were distributed across the possible 0-10 range of the score, median = 1.00,  $M = 1.57$ ,  $SD = 1.73$ . These initial estimates of phenotypic frequencies suggest that there will be sufficient proportions of participants to adequately power the analyses in this proposal.

**Power analysis.** Power calculations for the GCTA heritability analysis, which assumed an underlying

These analyses will be conducted with the GCTA software toolkit v1.26, using a restricted maximum likelihood method to compute a bivariate genetic relationship matrix by correlating the genetic similarity between each participant. Then, these genetic similarity estimates are modeled as random effects predictors of each phenotype: alcohol-influenced aggression, non-alcohol-influenced

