#### Analytic Plan

[S4S data will undergo the same GWAS and risk score procedures as employed in the discovery dataset.]

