#### Feasibility

This first phase of Aim II builds upon the already successful and ongoing S4S project, by simply adding a short online survey to the existing S4S battery of questionnaires. However, undergraduates at VCU differ from the [diverse members of the discovery sample] in ways that may suppress the amount of alcohol-influenced aggression among the S4S sample (e.g., lower levels of alcohol misuse and dependence). A pilot sample of VCU undergraduates were asked about their aggressive behavior and whether it occurred in the context of

alcohol misuse or not. Of the 166 female and male participants surveyed, 53.6% indicated that they had participated in a physical fight in the past 5 years (30.1% had been in more than 1 fight). Of those who had previously fought, 38.2% participated in this fight under the influence of alcohol. These initial estimates suggest that 1 out of 5 VCU undergraduates (i.e., 20.48%) have perpetrated a substantial act of physical aggression under the context of alcohol misuse. This prevalence rate indicates that the much larger pool of potential S4S participants is likely to exhibit alcohol-influenced aggression at a sufficient rate to test associations with polygenic risk scores.

Power analysis. The expected S4S sample size of 10,000 students will provide 80% power to detect a genome-wide effect of 0.35% variance explained in alcohol-influenced aggression, or larger. [The S4S GWAS is likely to be under-powered, yet performing this replication GWAS will serve as a valuable training in how to collect genomic data and use it to replicate previous GWAS results.]

Potential Problems and Alternative Strategies. The S4S sample GWAS may not replicate the profile of SNPs found in the [discovery] sample, as the S4S sample is smaller and is comprised of undergraduate students. However, replication is a crucial step in genomic science and this is as important training experience.

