#### Phase II - Investigating Neural Mechanisms in an S4S Sub-Sample

[figure not shown]
Participants. From the 2018-2020 cohorts of the S4S sample, I will recruit [202] individuals with low ( $N = 101$ ) and high ( $N = 101$ ) polygenic risk scores for alcohol-influenced aggression for a brain imaging experiment. Participants [will be equal numbers of males and females and] are expected to reflect the ethnic/racial makeup of the larger S4S sample which is relatively diverse (40% male, 60% female; 51% White, 19% African American, 15% Asian, 6% Hispanic/Latino, and 9% other/multiracial/unknown). Ages will range from 21-35 to ensure that only adults complete the study, that they can legally consume alcohol, and that aging effects do not influence our MRI data.

Recruitment and Screening. I will recruit VCU students who enrolled in the 2018-2020 cohorts of the S4S study, using their existing contact information in the S4S participant database. Participants will be recruited based on their polygenic risk scores that were obtained from the [discovery] GWAS. The S4S GWAS will not be used to establish the polygenic risk scores used to recruit these participants as they draw from the same pool of individuals. Establishing polygenic effects on behavior requires replication in an independent sample, as the use of dependent samples artificially inflates association statistics. Recruitment based on polygenic risk scores will proceed by contacting individuals from the lowest end of the distribution of polygenic risk scores (low risk group) and the highest end of the distribution of risk scores (high risk group), working from both ends of the distribution towards the median. Individuals who are contacted based on their risk scores will be screened with an online survey various conditions that would make the alcohol administration and MRI scanning procedures unsafe or invalid (see Protection of Human Subjects for a detailed list) and will be contacted to schedule an appointment if they pass these criteria.

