**Table 3. Research activities by award year (Y).**

Activity	Y1	Y2	Y3	Y4	Y5
[Discovery] data preparation	X				
[Discovery] data analysis	X	X			
[Discovery manuscript submission]			[X]		
S4S genotyping data collection	X	X			
S4S genotyping data analysis			X		
[S4S genotyping manuscript submission]			[X]		
S4S neuroimaging data collection			[X]	X	
S4S neuroimaging data analysis					X
[S4S neuroimaging manuscript submission]					[X]
R01 application preparation				X	X
[R01 application submission]					[X]

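### The risk-score threshold is chosen by maximum R², and the only sample named at that step is the discovery sample that supplies the p-values and weights

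*Combined protocol and SAP*

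**What the plan says.** - **Threshold rule.** Section C, discovery-sample Analytic Plan, GWAS paragraph: scores are formed from "SNPs meeting increasingly stringent significance thresholds: .5, .4, .3, .2, .1, .05, .01, .001, .0001. The threshold that maximizes the variance explained" in alcohol-related aggression is used. SNP weights are the GWAS effect estimates. The meta-analysis is said to return effects as per cent variance explained. No hold-out study, cross-validation or tuning set is named.
- **S4S, Phase I Analytic Plan:** "S4S data will undergo the same GWAS and risk score procedures as employed in the discovery dataset". As written, S4S also builds its own GWAS-weighted score.
- **S4S, Phase I Feasibility:** alcohol-influenced aggression is expected "at a sufficient rate to test associations with polygenic risk scores".
- **Phase II, Recruitment and Screening:** participants are picked from the two ends of the discovery-based score. "The S4S GWAS will not be used to establish the polygenic risk scores used to recruit these participants", and the same paragraph warns that dependent samples inflate association statistics.
- **SNP set.** Discovery genotypes are described "with samples imputed to 1000 Genomes"; no clumping or pruning step is stated.
- **Fallback.** If the discovery GWAS yields no significant SNP, a product of two external scores replaces this one. No cut-off for significance is given there.

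**The concern.** A score weighted by estimated SNP effects fits the noise of the people in whom those effects were estimated. Each further SNP admitted by a looser threshold brings its own fitted noise, so R² in that sample rises as the threshold loosens, whether or not the added SNPs carry signal. Used as a selection rule, it returns the loosest threshold and says nothing about which threshold predicts in new people.

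The score decides who enters the imaging study. If the trait is driven by relatively few variants, a score diluted by noise SNPs separates the low- and high-risk groups less well. That cannot be repaired after scanning. The same fault would affect replication: an R² from a score both weighted and tuned in S4S is an in-sample figure for S4S and does not test the discovery score.

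**Working it through.** The plan gives no R², chosen threshold or tuning-sample size, so there is no figure of its own to reproduce on this point. The discovery N does check: 2,909 + 17,783 + 2,900 + 1,044 + 6,487 = 31,123.

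**Step 1: in-sample R² with no genetic signal.** For M independent SNPs and two-sided threshold t, let c = z(1 − t/2), a(t) = t + 2c·φ(c) and A = (M/N)·a(t). Then R² = A/(1 + A).

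Inputs: N = 31,123 (Table 1); M = 100,000 (assumption); M/N = 3.213.

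- t = .5: c = 0.6745, a = 0.9287, A = 2.984, R² = 0.749.
- t = .0001: c = 3.891, a = 0.001703, A = 0.00547, R² = 0.005.

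| Threshold | .5 | .4 | .3 | .2 | .1 | .05 | .01 | .001 | .0001 |
|---|---|---|---|---|---|---|---|---|---|
| Null R² | 0.749 | 0.737 | 0.716 | 0.676 | 0.585 | 0.473 | 0.214 | 0.039 | 0.005 |

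R² at p<.5 is 0.60 for 50,000 SNPs and 0.86 for 200,000. The GCTA paragraph says that "any two participants who share a second-cousin degree of relatedness or more will be excluded from subsequent analyses". If that halved N (assumption), the values for 100,000 SNPs would be 0.86 and 0.01. The maximum is at p<.5 in every case.

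**Step 2: does it persist with signal, a skewed outcome and LD?** Simulation with N = 1,000 and M = 3,200 (M/N about 3.2, as above), linear weights, and an independent test sample of equal size. Seven scenarios of 60 runs covered: no signal; h² = 0.2 (the plan's GCTA value) with 0.3%, 1% or 50% of SNPs causal; a 0–10 count outcome matched to the COGA mean of 1.57 and SD of 1.73; a small SNP set (M = 300); and LD blocks. The in-sample rule picked p<.5 in 420 of 420 runs. With 0.3% causal, in-sample R² was 0.764 at p<.5 and 0.187 at p<.0001, while out-of-sample R² was 0.014 and 0.168.

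The limit is extreme unpruned LD. With 2,000 independent SNPs plus 15,000 null SNPs in blocks of 100 (adjacent r = .99), p<.5 was picked in only 2 of 10 runs and little was lost (out-of-sample R² 8.1% against 8.6% under 5-fold cross-validation).

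**Step 3: what it costs the score.** Small-scale runs, independent SNPs, h² = 0.2, 1% causal; out-of-sample R²:

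| Weights | In-sample choice | Cross-validated choice |
|---|---|---|
| Linear per-allele effects | 0.8% | 7.4% |
| Squared (variance-explained scale) | 4.2% | 6.6% |

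At 3% causal the loss was small or nil (0.9% against 1.2% in one set with linear weights; none in another). At 10% or more causal there was none.

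**Step 4: illustration for group separation.** Take d = 2·i·√R²·r, with i = 1.755 for 10% tails, r the trait–laboratory correlation, 99 per group (Phase II power analysis), and a two-sided t-test at .05. The tails and r are assumptions.

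- Linear, r = 0.5: R² = 0.008 gives d = 0.157 and power 20%; R² = 0.074 gives d = 0.477 and power 92%.
- Squared, r = 0.5: R² = 0.042 gives d = 0.360 and power 71%; R² = 0.066 gives d = 0.451 and power 88%.
- With r = 0.3 these become 10% against 52%, and 33% against 47%.

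Not modelled: the quasi-Poisson fit, the multi-ancestry meta-analysis, matching of the groups, and the planned mixed-effects and mediation analyses.

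**The case against.** The strongest reply is that the plan nowhere says R² will be computed in the weight-giving sample. A reader might infer that in-sample tuning is the stated procedure; it is not. Recruitment and Screening shows that the investigator knows the hazard of dependent samples. It bars only the S4S GWAS from setting the recruitment score, Phase I Feasibility foresees testing risk scores in S4S, and Table 3 puts "S4S genotyping data analysis" in Y3, the year imaging starts. So tuning in S4S is possible. This stands as a limit on the claim, but it does not close the gap: no sentence gives S4S that task. S4S would also be an awkward choice, because the aggression items are collected only in the 2018–2020 cohorts that supply the scanned participants, and S4S is the replication sample.

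The second reply concerns size. If the variance-explained effects are used literally as weights, noise SNPs are shrunk and the loss is far smaller. This stands, and it is why both scales are shown. The causal fraction is assumed throughout, and the group t-test is not the planned analysis.

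Third, the fallback may replace this score. How often depends on a significance cut-off that the fallback paragraph does not give. At the .05 used in the GWAS power calculation it would almost never apply. At 5e-8 it would usually apply for highly polygenic traits, where nothing is lost anyway.

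**Conclusion.** The point holds as a conditional one. The sample for choosing the threshold is not named, and the text most naturally points to the discovery sample. If that reading is followed with independent or clumped SNPs, the choice of p<.5 is close to automatic and uninformative. Extreme unpruned LD can change the pick, so an unconditional claim that p<.5 will be chosen would go too far.

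The harm is a weaker recruitment score when the trait is sparse. Its size depends on the causal fraction and the weight scale: a large loss at 1% causal with linear weights, a moderate one with squared weights, and little or none for a highly polygenic trait. A reader might infer that Phase II would produce false positives. It would not: the imaging participants are independent of the discovery sample, so type I error is unaffected. The power figures illustrate direction only and are not estimates of this study's power.

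Separately, the Phase I plan as written gives an in-sample R² in S4S, which is not a replication of the discovery score. Both matters should be settled before any score is computed.

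**What to change.** **Discovery Analytic Plan, GWAS paragraph.** Replace the threshold sentence with: the threshold is the one with the highest R² in discovery participants not used to estimate the p-values and weights (5-fold cross-validation or leave-one-study-out across the five Table 1 studies), on LD-clumped SNPs, with p-values and weights re-estimated in each training set and any retained relatives kept in one fold. State that the weights are signed per-allele effects. Re-estimate the weights in the full discovery sample, and fix the score before it is applied to S4S.

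**Phase I Analytic Plan.** State that replication is the R² of that fixed discovery score in S4S, not of a score weighted and tuned in S4S. If tuning in S4S was intended, say so, use members who will not be scanned, and do not call the tuned R² an independent replication.

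**Cost.** A few sentences and about five extra GWAS runs on data already held. The reported R² will be much smaller. For a highly polygenic trait there is no gain, and at small N the cross-validated choice is slightly noisier: at N = 3,112 its out-of-sample R² was 0.56–0.67%, against 0.88% for the in-sample choice. That loss was not seen at N = 31,123.

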#### **Feasibility**

Preliminary phenotypic analyses on the alcohol-influenced aggression scores from the COGA dataset, assessed among a subset of 9,273 participants, revealed a substantially-variable, albeit positively-skewed, distribution of alcohol-influenced aggression (Figure 3). Scores were distributed across the possible 0-10 range of the score, median = 1.00,  $M = 1.57$ ,  $SD = 1.73$ . These initial estimates of phenotypic frequencies suggest that there will be sufficient proportions of participants to adequately power the analyses in this proposal.

**Power analysis.** Power calculations for the GCTA heritability analysis, which assumed an underlying

These analyses will be conducted with the GCTA software toolkit v1.26, using a restricted maximum likelihood method to compute a bivariate genetic relationship matrix by correlating the genetic similarity between each participant. Then, these genetic similarity estimates are modeled as random effects predictors of each phenotype: alcohol-influenced aggression, non-alcohol-influenced

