## SPECIFIC AIMS

Aggressive behavior in the context of alcohol misuse is a substantial public health concern. Genetic predispositions have been identified for both aggression and alcohol misuse. However, the biological factors that predispose individuals towards alcohol-influenced aggression remain poorly understood. Specifically, the extent to which alcohol-influenced aggression is genetically-influenced is unknown. Further, it remains to be seen whether alcohol-influenced aggression is uniquely heritable, or is simply the by-product of genetic risk factors for both alcohol misuse and aggression. If alcohol-influenced aggression is found to be substantially genetically-influenced, the specific genetic and neural pathways through which these effects are transmitted must then be investigated. The goal of the research activities in this K01 proposal is to fill these gaps in our knowledge.

[figure not shown]
The overall objective of the research activities in this K01 award proposal is to examine the genetic factors and neural mechanisms that promote alcohol-influenced aggression. The proposed research activities will address the following research aims and test their associated hypotheses:

**Aim 1: Examine the extent to which genetic factors influence the extent to which individuals act aggressively in the context of alcohol misuse.** *Hypothesis 1:* Genome-wide complex trait analysis (GCTA) will reveal that alcohol-influenced aggression exhibits substantial genetic heritability.

**Aim 2: Examine whether genetic factors for alcohol-influenced aggression exist above-and-beyond genetic risk factors for general aggressiveness and alcohol misuse.** *Hypothesis 2:* After statistically controlling for genome-wide associations with non-alcohol-influenced aggression and alcohol misuse, significant genetic heritability will still be observed for alcohol-influenced aggression via GCTA.

**Aim 3: Identify the specific genetic loci and polymorphisms that are most strongly linked to alcohol-influenced aggression and create polygenic risk scores from these findings.** *Hypothesis 3:* Genome-wide association study (GWAS) techniques will identify specific gene polymorphisms associated with alcohol-influenced aggression.

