#### Analytic Plan

Genome-wide complex trait analyses (GCTA). The initial analysis of the [discovery] dataset will seek to decompose phenotypic variance into the proportions that can be explained by genetic ( $h^2$ ) and

environmental/measurement-error factors. GCTA will quantify the heritability of aggressive, alcohol-misusing, and alcohol-aggressive phenotypes. GCTA will then be applied to determine the extent whether alcohol-influenced aggression has distinct heritability from general aggression and alcohol misuse (Figure 2A) or shares substantial genetic overlap with these two related phenotypes (Figure 2B).

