**Figure 3. Frequencies of a subset of COGA participants' alcohol-influenced aggression scores.**

heritability of  $h^2 = 0.2$ , a type I error rate of 0.05, and a variance of SNP-derived genetic relationships of .00002, suggested that 80% power for the proposed GCTA can be obtained with 4,430 participants. The [discovery] sample far exceeds this sample size at over [31,000] participants. GWAS power analyses, implemented via the GWAS.PC v1.0 package for R statistical software were also performed to determine the minimum effect size (in units of % variance explained) that [the discovery sample could detect with 80% power. Calculations were based on the planned detection of multiple, additive SNP markers, an alpha level of .05, and a minor allele frequency of 0.05, revealing that the proposed GWAS is able to detect effect sizes of 0.09% variance-explained and larger. However, this is likely an optimistic assessment as this power analysis did not account for the moderating effects of ethnicity/race and the genetic relatedness of participants (yet recent research has indicated that GWAS power is not significantly affected by underlying genetic relationships between participants).]

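### The Aim 2 rule for a unique genetic basis is not tied to a conditional heritability: the GCTA models named report total h², which can pass 0.1 even under complete genetic overlap

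*Combined protocol and SAP*

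**What the plan says.** Hypothesis 2 (Specific Aims) is: "After statistically controlling for genome-wide associations with non-alcohol-influenced aggression and alcohol misuse, significant genetic heritability will still be observed". The discovery-sample Analytic Plan sets this against the rival model of Figure 2B, in which the trait "shares substantial genetic overlap with these two related phenotypes".

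The GCTA text is split in the extracted document; it starts in the Analytic Plan, continues under Feasibility and ends under the Figure 2 caption. Rejoined, it names GCTA v1.26, "using a restricted maximum likelihood method to compute a bivariate genetic relationship matrix by correlating the genetic similarity between each participant". After that, "these genetic similarity estimates are modeled as random effects predictors of each phenotype", the phenotypes being alcohol-influenced aggression, non-alcohol-influenced aggression and alcohol misuse. On adjustment: "Fixed-effects covariates will include age, ethnicity/race, sex, and socioeconomic status".

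The text then says that the h² of alcohol-influenced aggression is estimated while controlling "for the heritability of non-alcohol-influenced aggression and alcohol misuse phenotypes". A value above 0.1 with p < .05 "for alcohol-influenced aggression will serve as support for the unique genetic basis for this phenotype". It gives no formula, variance component, genetic-correlation estimate or standard error for the controlled quantity.

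**The concern.** In a single-trait or bivariate REML model, a trait's h² is its whole SNP-based genetic variance divided by its phenotypic variance. Genetic covariance with a second trait is a separate parameter and is not subtracted. The h² that these models print is therefore the same whether the genetic basis is distinct (Figure 2A) or shared (Figure 2B).

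The plan fixes a threshold and an interpretation but does not say which quantity is compared with the threshold. This is the only stated test of Aim 2. If the printed h² is used, Hypothesis 2 can be confirmed when the unique part is zero.

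**Working it through.** **Inputs from the power analysis under Feasibility.** h² = 0.2, "a type I error rate of 0.05", variance of genetic relationships .00002, 80% power, N = 4,430. Discovery N = 31,123 (Table 1), of which COGA is 17,783. N after the relatedness exclusion is not given.

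**1. Reproduce the plan's figure.** SE(h²) = √(2 / (N² × .00002)) = 316.2 / N. The required N is 316.2 × (1.960 + 0.842) / 0.2 = 4,430, which matches with two-sided alpha (one-sided gives 3,931). The calculation is for a single trait's total h². No genetic correlation enters it.

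**2. Apply the rule to the reported (total) h² when overlap is complete.** Take total h² = 0.2 and unique h² = 0. The rule is met when the estimate exceeds the larger of 0.1 and 1.96 × SE (normal approximation).

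| N | SE | Probability rule is met |
|---|---|---|
| 4,430 (plan's required N) | 0.0714 | 0.80 |
| 9,273 (COGA subset with preliminary phenotype data) | 0.0341 | 0.998 |
| 13,340 (= 31,123 − 17,783, no COGA) | 0.0237 | near 1 (threshold 0.1 / 0.0237 = 4.2 SE below 0.2) |
| 31,123 (before exclusions) | 0.0102 | near 1 |

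**3. What the conditional quantity would be.** Unique h² = h² × (1 − r′R⁻¹r). Here r holds the genetic correlations of the target with the two other traits, and R is the genetic correlation matrix of those two. With total h² = 0.2 and assumed correlations (target with first, target with second, first with second):
- Correlations 0.5, 0.5, 0.2: r′R⁻¹r = (0.25 + 0.25 − 0.10) / 0.96 = 0.417, so unique h² = 0.117.
- Correlations 0.8, 0.6, 0.3: r′R⁻¹r = (0.64 + 0.36 − 0.288) / 0.91 = 0.782, so unique h² = 0.044.
- Complete overlap: unique h² = 0.

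Total h² is 0.2 in all three cases.

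**4. Check by simulation.** 40 runs used 1,500 people, 600 SNPs, a target trait with h² 0.2 and one comparison trait with h² 0.3, at genetic correlation 1. Mean h² of the target was 0.195 (single-trait likelihood) and 0.201 (bivariate likelihood). The mean estimated genetic correlation was 0.97 and the mean residual h² 0.013. The rule on the single-trait h² was met in 40 of 40 runs; the residual exceeded 0.1 in 0 of 40. This confirms which quantity the models return. It does not mimic the plan's precision.

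**5. The other natural reading of controlling: the two phenotypes as covariates.** Complete overlap (all genetic correlations 1), total h² = 0.2, both other traits with the same h². Other-trait h² and environmental correlations are assumed. Entries are the adjusted h².

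| Environmental correlation | Other-trait h² 0.1 | 0.2 | 0.4 |
|---|---|---|---|
| 0 | 0.139 | 0.095 | 0.041 |
| 0.2 | 0.101 | 0.055 | 0.012 |
| 0.4 | 0.084 | 0.031 | 0.000 |

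First cell by hand: each covariate has coefficient √0.02 / 1.1 = 0.1286. The genetic part left is (√0.2 − 2 × 0.1286 × √0.1)² = 0.134. The residual variance is 1 − 2 × 0.1414 × 0.1286 = 0.964. The ratio is 0.139. Covariate adjustment removes phenotypic association, so some shared genetic variance stays behind.

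**The case against.** The strongest reply is that the plan does not say it will test total h². It says the estimate controls for both traits, and Hypothesis 2 says the same. A correctly computed residual would be zero under full overlap, and the rule would work. This stands: the probabilities in step 2 hold only if the threshold is applied to the h² that the named models print.

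Bivariate REML also estimates genetic covariance, so three pairwise runs would supply everything needed. This stands too. The named software can provide the inputs; the derivation and its test are missing.

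The N of 31,123 is taken before relatives are removed, and COGA and COGEND include relatives. A margin of about 10 standard errors (0.1 / 0.0102) is therefore not the analysis-set figure. Without COGA it is about 4, with the same direction.

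The covariate list need not be exhaustive, so the two phenotypes might be added. Step 5 shows that this gives no protection in part of the assumed range. Figure 2 is not shown, but its caption calls the models conceptual, so it probably does not define an estimator.

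Finally, the GWAS follows the GCTA with no condition on its result, so Aims 3 and 4 do not depend on this rule.

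**Conclusion.** The concern holds in a conditional form. The plan states an intention to control for two traits, but none of the models it names produces the controlled heritability that its rule requires. If total h² is used, complete overlap passes with probability about 0.80 at N = 4,430 and near 1 at 13,340 or more. These figures rest on the plan's h² of 0.2, its relationship variance of .00002 and a normal approximation. If the phenotypes are covariates, the adjusted h² under complete overlap lies between about 0 and 0.14, so whether it passes depends on heritabilities and environmental correlations that the documents do not give.

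A reader might infer that the plan will almost always declare a unique basis, or that its rule cannot separate Figure 2A from Figure 2B. The documents do not support that, because they do not say that the uncontrolled h² is the quantity tested. A reader might also infer that a three-trait model is indispensable; three pairwise models are enough. Still, this is more than missing detail: two natural ways of carrying out the text can confirm Hypothesis 2 when it is false.

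**What to change.** In the GCTA text under the Figure 2 caption, define the Aim 2 quantity:

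- Estimate the 3×3 genetic covariance matrix G (trait 1 = alcohol-influenced aggression) from three pairwise bivariate REMLs or one trivariate REML.
- Define unique h² = (G₁₁ − G₁,₂₃ G₂₃,₂₃⁻¹ G₂₃,₁) / phenotypic variance of trait 1, and apply both the 0.1 threshold and the test to it.
- Use a jackknife or a boundary-aware test, because the unique variance is at zero under full overlap. State a fallback if G₂₃,₂₃ is near-singular: a generalised inverse, or conditioning on a single comparison trait.
- Report the genetic correlations beside the estimate.
- In the power analysis, state that 4,430 participants applies to total h² (Aim 1) and not to the Aim 2 quantity. Power for unique h² would need a separate calculation over a range of assumed genetic correlations, at the N left after relatives are excluded.

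No new data are needed. The cost is some post-processing and a larger standard error for the unique part than for total h².
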